HIPAA	Health Insurance Portability and Accountability Act
HIV	Human Immunodeficiency Virus
ICF	Informed Consent Form
IRB	Institutional Review Board
LAR	Legally Authorized Representative
LUTS	Lower Urinary Tract Symptoms
MOP	Manual of Procedures
NIDDK	National Institute of Diabetes and Digestive and Kidney Diseases
NIH	National Institutes of Health
PI	Principal Investigator
PUSH	Preventing Urinary Stones with Hydration
RBM	Risk-Based Monitoring
SPS	Structured Problem Solving
SDRC	Scientific Data Research Center
UOP	Urine Output
USD	Urinary Stone Disease
USDRN	Urinary Stone Disease Research Network
WTH	Way to Health

STATEMENT OF COMPLIANCE

I have read the protocol, including all appendices, and I agree that it contains all necessary details for me and my staff to conduct this study as described. I will personally oversee the conduct of this study as outlined herein and will make a reasonable effort to complete the study within the time designated.

I will provide all study personnel under my supervision with copies of the protocol. I will discuss this material with them to ensure that they are fully informed about the efficacy and safety parameters and the conduct of the study in general. I am aware that, before beginning this study, the Institutional Review Board responsible for such matters must approve this protocol in the clinical facility where it will be conducted. I agree to make all reasonable efforts to adhere to the attached protocol.

I agree to provide all study participants with informed consent forms, as required by government and International Conference on Harmonization regulations. I further agree to report to the sponsor any adverse experiences in accordance with the terms of this protocol.

Principal investigator Name (print)

[figure not shown]
Signature

Date

PROTOCOL SUMMARY

Protocol Number	USDRN01
Protocol Title:	Prevention of Urinary Stones with Hydration (PUSH)
Main Criteria for Inclusion:	Study participants \geq 12 years of age with \geq 1 symptomatic stone event in past 3-5 years
Study Objectives:	To determine whether a multi-component program of behavioral interventions will result in reduced risk of stone disease recurrence/progression over a 2 year period.
Study Design:	Randomized, blinded, prospective clinical trial
Intervention Regimen	Behavioral intervention program
Duration of Study Participation	24 months
Duration of Study Overall	4 years
End-of-study Definition	Last study participant completion of 24-month follow-up
Number of Study Participants	Approximately 1642
Number of Clinical Centers:	6
Primary Endpoint:	Symptomatic stone event
Secondary Endpoints:	Asymptomatic stone recurrence Stone growth Fluid intake adherence Urine volume Cost identification

SCHEMATIC OF STUDY DESIGN

2 INTRODUCTION: BACKGROUND INFORMATION AND SCIENTIFIC RATIONALE

2.1 BACKGROUND INFORMATION

Urinary stone disease (USD) in the United States is an important medical, scientific, and public health problem. The prevalence of urinary stones has nearly doubled in the past 15 years¹ and health care utilization for treating patients with stones has risen in parallel.^{2,3} USD affects 1 in 11 persons in the United States, a prevalence similar to that of diabetes.¹ Estimates from the Urologic Diseases in America project suggest that aggregate expenditures for treating study participants with urinary stones exceeds \$10 billion, making USD one of the most expensive urologic conditions.²

Fluid intake is an appealing intervention for the secondary prevention of USD because it is effective, low risk, and inexpensive.⁴⁻⁷ In a randomized trial of adults with urinary stones, fluid intake that resulted in a urine output greater than 2L/day decreased stone recurrence by 55% and increased the time to recurrence by more than 1 year.⁴ Although stone formers are routinely counseled to drink more fluids, the average increase in 24-hour urine volume among adults with USD is only 300mL,⁸ suggesting that adherence to fluid intake recommendations is low even when the risks of non-compliance are severe. Identifying ways to change behaviors to decrease USD recurrence is an area in need of research.⁹

2.2 RATIONALE

Most therapies for USD are directed toward treating an acute stone episode. Review of current prevention-focused guidelines reveals substantial divergence on recommendations by different organizations and a surprising number of recommendations based on expert opinion.^{10,11} Current guidelines do agree, however, on one fundamental lifestyle change for USD prevention: maintaining a high oral fluid intake resulting in high urine output (UOP). Therefore, an interventional trial targeting adherence to high oral fluid intake offers potential for supporting novel secondary prevention strategies for USD patients.

Substantial evidence exists for the efficacy of adherence interventions grounded in Contingency Management Theory and behavioral economics. For example, appropriately structured financial incentives (FI) can lead to improvements in smoking cessation,¹²⁻¹⁵ weight loss,¹⁶⁻¹⁹ substance abuse management²⁰⁻²² and medication adherence.²³⁻²⁵ The Contingency Management perspective on behavior change is built upon B.F. Skinner's²⁶ studies of operant conditioning, which showed how many behaviors are acquired and reinforced by environmental contingencies. Contingency Management therefore attempts to modify behavior by changing the consequences of the behavior.²⁷ In a complementary way, behavioral economics research has examined how common decision errors contribute to health risk behaviors, such as lack of fluid intake, and suggests ways in which these decision-errors can also be used to structure successful interventions to improve health. We will apply FI to help maintain high fluid intake among USD study participants.

Other behavior change research has examined Structured Problem Solving (SPS) as a means to improve medication adherence and self-management.²⁸⁻³⁰ SPS addresses behavior change by: a) identifying personal barriers to change, b) identifying feasible solutions the patient is able to implement, and c) continually evaluating the efficacy of the approach. Some studies have examined the role of self-monitoring, social interventions (e.g., peer feedback, team competition) and device-based reminders to improve adherence behaviors. While many of these interventions have been evaluated in isolation and over relatively short durations (<1 year), a key unanswered question is whether these interventions can be integrated to foster durable behavior change.

Increasingly, researchers are conducting pragmatic, multi-component trials to improve outcomes and care delivery.³¹⁻³³ Therefore the proposed study will test a theory-based program of interventions directed towards maintaining a high fluid intake. A key secondary goal of the proposed trial will be to add to the evidence base regarding fluid for prevention of urinary stones. Existing guideline recommendations for increased fluid intake to prevent stones derive from two randomized clinical trials (RCT) of increased fluid intake.^{4,34} One RCT demonstrated a reduced risk of stone formation (RR 0.45, 95% CI 0.24 – 0.84) over a five year period,⁴ although the trial has been rated as poor quality due to unclear allocation concealment, lack of blinding and use of analytic methods that did not adhere to intention-to-treat principles.³⁵ The other randomized trial provided insufficient evidence regarding the intervention due to a low number of outcome events.³⁵ Both trials included only adult study participants, and therefore the generalizability of fluid intake for secondary stone prevention among children remains unclear. Thus, an important gap in evidence exists for a key component of guideline-based secondary prevention.

2.3 POTENTIAL RISKS AND BENEFITS

2.3.1 KNOWN POTENTIAL RISKS

The research involves the collection of protected health data. There is a small risk of loss of confidentiality but the researchers have in place several mechanisms for reducing this risk as described below (see section 13.4). There is also a potential risk of water intoxication leading to hyponatremia. The likelihood for this event is low, but theoretically possible. The investigators will mitigate this risk by excluding study participants with a prior history of hyponatremia or diseases and conditions predisposing an individual to hyponatremia. Furthermore, study participants will be counseled regarding the risk of hyponatremia from consumption of water beyond the recommended volume, as well as symptoms and consequences of severe hyponatremia.

2.3.2 KNOWN POTENTIAL BENEFITS

All participants in PUSH will receive educational information on the importance of fluid intake. Through participation in this study, each participant will have the potential to increase their fluid intake, which could improve their health and reduce their risk for future USD. If this approach is effective, it could have tremendous benefits for society if adopted on a wide scale to help individuals increase fluid intake

after experiencing a urinary stone event. It is expected that other people will gain knowledge from this study and that participation could help clinicians and study participants understand how to effectively motivate increased fluid intake and reduce the risk of kidney stones.

Children and families, as well as adult participants, will have the benefit of volunteerism. The medical, physical and social risks are minimal for all participants and are small in relation to the anticipated benefits of the knowledge to be gained. Additionally, the information that is obtained will be disseminated as widely as possible, including through submission for publication in peer-reviewed journals, presented at scientific conferences, and the many dissemination channels of the NIDDK and academic institutions involved. The results of this study may provide data for future studies that will lead to interventions that influence the development, management, and long-term outcomes for pediatric and adult study participants with USD. It is also possible that the information obtained because of this project will be used to develop clinical practice guidelines, which could directly benefit patients with USD in the future.

3 OBJECTIVES AND PURPOSE

The primary aim of the study is to determine whether a multi-component program of behavioral interventions to increase fluid intake will result in reduced risk of stone disease progression over a 2-year period. Under this aim, the study will test the following specific hypotheses, comparing 1) intervention arm: individuals participating in a multi-component program of behavioral interventions targeting increased fluid intake (sufficient to achieve a urine output ≥ 2.5 L daily or ≥ 30 mL/kg/day for those study participants aged < 18 years and weighing < 75 kg); versus 2) control arm: individuals receiving usual care:

- a. **Primary hypothesis:** Participants in the intervention arm will have a reduced risk of symptomatic stones over 2 years.
- b. **Secondary hypothesis #1:** Participants in the intervention arm will have a reduced risk of stone disease progression (a composite outcome comprising symptomatic stone events, new asymptomatic stone on imaging, or stone growth of at least 2 mm on imaging) over 2 years.
- c. **Secondary hypothesis #2:** Participants in the intervention arm will have a reduced risk of forming new asymptomatic renal stones over 2 years.
- d. **Secondary hypothesis #3:** Fewer participants in the intervention arm will exhibit growth in existing renal stones of at least 2 mm on imaging over 2 years.
- e. **Secondary hypothesis #4:** Participants in the intervention arm will be more likely to achieve goal 24-hour urine output.
- f. **Secondary hypothesis #5:** Participants in the intervention arm will be more likely to develop lower urinary tract symptoms (LUTS).
- g. **Secondary hypothesis #6:** Greater urine output will be associated with reduced risk of stone disease progression, controlling for medication use (time updated), disease severity and clinical characteristics (e.g., body mass index).

h. **Secondary hypothesis #7:** Participants with pre-existing LUTS will be less likely to achieve 24-hour urine output goals as compared to those without pre-existing LUTS.

4 STUDY DESIGN AND ENDPOINTS

4.1 DESCRIPTION OF THE STUDY DESIGN

This is a two arm randomized controlled trial that incorporates pragmatic features, an adaptable intervention, patient choice, and remote monitoring of fluid intake through a “smart” water bottle. The study period is 24 months and will enroll approximately 1642 participants. Randomization will be stratified within a clinical center by (adult vs. adolescent) and (first time vs. recurrent stone former). Intervention and control arm study participants will receive a smart water bottle that records daily fluid consumption, usual care including guideline-based recommendations of adequate fluid intake to decrease kidney stone recurrence, and periodic 24 hour urine collections.

Participants in the intervention arm will receive an individualized “fluid prescription”, which will be the additional volume of fluid intake needed to maintain a urine output of at least 2.5 L/day for study participants aged at least 18 years (adults) or 30 mL/kg/day for study participants aged 12-17 years inclusive (adolescents) and weighing < 75 kg; this additional fluid will be consumed from the smart water bottle. The prescription will be determined by the following equation: Initial Fluid Prescription = $1.2 \times (2.5L - \text{median urine volume on all 24-hour urine collections in the 12 months prior to enrollment})$. The fluid prescription may be modified, as needed, based on the 24-hour urine volume measurement obtained approximately 2 weeks after randomization. To reduce risk of unblinding treating providers, adjustments to the fluid prescription will be communicated by the study coordinator. The intervention arm also includes a behavioral program that consists of financial incentives and structured problem solving (SPS) to maintain the recommended fluid intake. The intervention period can be divided into phases of “induction,” “consolidation,” “taper,” and “maintenance.” The induction phase comprises the first 6 months of the intervention, and will initially include eligibility for FI on 100% of days. During induction, the intensity of the intervention can be increased for those study participants who do not consistently meet daily fluid intake goals by adding structured problem solving (SPS) to help participants develop feasible solutions to overcoming personal barriers to maintaining the prescribed fluid intake. The consolidation phase comprises the second 6 months and enables some additional potential for SPS-based adaptation of the intervention, but the frequency of the financial incentives will be slightly lower. The taper phase will comprise months 13 – 18, during which SPS is withdrawn and financial incentives are fully tapered. In the final 6-month maintenance phase, participants will have access only to “low touch” and low cost interventions (e.g., text reminders) that the participant selected to help sustain new habits of fluid consumption.

Participants in the control arm will receive standard care instructions according to American Urological Association (AUA) guidelines to increase overall fluid consumption to achieve UOP of at least 2.5 L daily. They will also receive a “smart” water bottle with capability to self-monitor their fluid intake, though the use of the “smart” water bottle is optional in the control arm. Approximately 2 weeks after randomization, a 24-hour urine volume measurement will be obtained, to provide control arm

participants with initial feedback as to whether or not they are meeting the urine output goal (urine output \geq 2.5 L daily or 30 mL/kg/day for those study participants <75 kg aged less than 18 years). Participants in the control arm will not receive additional incentives, but will receive monetary compensation for completion of study activities (e.g., urine collections, study-related imaging, and study completion).

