6 STUDY INTERVENTION

6.1 STUDY INTERVENTIONS AND CONTROL DESCRIPTION

6.1.1 OVERVIEW

	Control	Intervention
Platform	Participants will be provided with a wireless-enabled “smart” water bottle. Participants will be allowed, but not required, to use or sync the water bottle with their mobile device	Wireless-enabled “smart” water bottle Participants must sync water bottle with their mobile device daily
Fluid Goal	Usual care (sufficient fluid intake to achieve UOP \geq 2.5L per 24 hours or 30/ml/kg/day for participants <18 years and <75 kg)	120% of baseline UOP deficit via the water bottle, with modification possible at Week 2; 24-hour urine volume check @ 2 weeks, 6 months, 12 months, and 18 months.

	Control	Intervention
	24-hour urine volume check @ 2 weeks, 6 months, 12 months, and 18 months.	

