- Renal ultrasound (if age <18) performed in the 3 months prior to the baseline visit

Provided that

- They are reviewed by the Investigator and deemed comparable to the imaging that would have been completed at baseline, with views in 3 dimensions.
- The participant has not had a stone passage event or removal procedure since the completion of the scan.

In order to facilitate recruitment, the Baseline imaging, and the associated pregnancy test for adult females, may be waived for participants:

- Enrolled and randomized from locations other than the 6 primary Clinical Centers/study sites
- Enrolled from an existing Clinical Center/site, but who are otherwise eligible but are refusing participation in the study because of imaging

The waiver of imaging will be documented in the study database. Adult female participants will be asked to verbally confirm that they are not pregnant or planning to become pregnant during their time in study.

All participants will be randomized to either the intervention arm or the control arm. Participants in the intervention arm will receive a smart water bottle, and will create accounts with Hidrate Spark, Way to Health, and in the EDC database, and will receive their initial fluid prescription. Participants in the control arm will receive the smart water bottle but will not be required to create a Hidrate Spark account; they will however be required to create Way to Health and EDC database accounts.

Note: The screening and baseline visits may be combined into a single, in-person visit, provided that:

1. Informed consent is obtained from the participant prior to any study procedures or collection of data in the EDC database.
2. Participant eligibility must be confirmed by the Investigator prior to randomization.

2 Weeks After Randomization

At 2 weeks (\pm 7 days) post-randomization, participants in intervention and control arms will complete a 24 hour urine collection, include volume and panel. In the intervention arm, this 24 hour urine total volume may be used to adjust the initial fluid prescription. In the control arm, study participants will be notified that their 24-hour urine total volume is at or above the target volume (2500 mL/24 hours or 30 mL/kg for those study participants <75kg aged less than 18 years) or below the target volume, and advised about their fluid intake in accordance with guideline-based recommendations of adequate fluid intake.

Follow-Up Procedures

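### The initial fluid-prescription equation uses a fixed 2.5 L for everyone, so participants under 18 and under 75 kg are prescribed over 300 mL/day more than their stated goal implies

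*Combined protocol and SAP*

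**What the plan says.** In section 4.1 the prescription is the additional drinking, taken from the smart bottle, required to hold urine output at 2.5 L/day in adults or at "30 mL/kg/day for study participants aged 12-17 years inclusive (adolescents) and weighing < 75 kg". The equation follows at once: "The prescription will be determined by the following equation: Initial Fluid Prescription = $1.2 \times (2.5L - \text{median urine volume", the median being taken over collections in the year before enrollment. It has no adolescent version, there or elsewhere in the protocol.

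The weight-based goal recurs in several places:

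- **Section 3**, describing the intervention arm: "urine output ≥ 2.5 L daily or ≥ 30 mL/kg/day for those study participants aged < 18 years", limited there to those under 75 kg.
- **Section 4.1**, control-arm feedback: "30 mL/kg/day for those study participants <75 kg aged less than 18 years".
- **Section 6.1.1**, Fluid Goal row, control column: "2.5L per 24 hours or 30/ml/kg/day for participants <18 years and <75 kg".
- **Section 7.1.1**, Week 2 notification of control participants: "2500 mL/24 hours or 30 mL/kg for those study participants <75kg aged less than 18 years".

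The intervention column of the same row in 6.1.1 says only "120% of baseline UOP deficit via the water bottle, with modification possible at Week 2" and does not name the goal from which the deficit is measured. On later correction, section 7.1.1 says that in the intervention arm "this 24 hour urine total volume may be used to adjust the initial fluid prescription".

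**The concern.** One sentence sets a goal per kilogram for younger, lighter participants, and the next computes the dose from an adult constant. Anyone applying the equation literally doses these participants toward 2.5 L/day whatever their weight.

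The prescribed volume drives the intervention. Under section 6.1.2 a participant keeps $1.50 for an incentive day only if that volume is drunk from the bottle. Under 6.1.3, failing the daily fluid goal too often over two 14-day periods brings in SPS, with boosters to follow. A 15-year-old who drinks enough to meet the protocol's own urine goal could therefore forfeit incentives and be counseled for non-adherence.

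The arms would also work to different standards: control adolescents under 75 kg are told whether they meet 30 mL/kg, while intervention adolescents of the same weight are dosed toward 2.5 L. Age group (adult or adolescent) is a randomization stratification factor (section 4.3) and a planned subgroup (section 10.4.8).

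**Working it through.** The plan gives no adolescent prescription to reproduce, so the check compares the equation with the definition that precedes it.

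**Inputs**

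- Goal for participants under 18 and under 75 kg: 30 mL/kg/day (sections 3 and 4.1).
- Equation: 1.2 × (2500 − m) mL/day, where m is the median prior 24-hour urine volume (section 4.1).
- Eligibility ceiling for this group: m below 25 mL/kg/day (sections 4.4, 5.1 and 7.1.1). The deficit to 30 mL/kg is therefore always positive, at more than 5 mL/kg.
- Weight w: the documents give no distribution, so the weights below are assumed for illustration.

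**Formulas**

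- As written: P1 = 1.2 × (2500 − m).
- Against the stated goal: P2 = 1.2 × (30w − m).
- Excess: P1 − P2 = 1.2 × (2500 − 30w). The baseline m cancels.

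**Bound without assumptions.** The excess falls as w rises. At w = 75 it is 1.2 × (2500 − 2250) = 300 mL/day. Since w is strictly below 75, the excess is always above 300 mL/day. The two targets coincide only at 2500 / 30 = 83.3 kg, outside the subgroup. Put per kilogram, the equation aims at 2500 / w, which is above 2500 / 75 = 33.3 mL/kg throughout, against a stated 30.

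**Illustration, with m set at the 25 mL/kg ceiling**

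| Weight (kg) | m (mL) | As written, P1 (mL/day) | Against 30 mL/kg, P2 (mL/day) | Excess (mL/day) | Implied target (mL/kg) |
|---|---|---|---|---|---|
| 40 | 1000 | 1800 | 240 | 1560 | 62.5 |
| 50 | 1250 | 1500 | 300 | 1200 | 50.0 |
| 60 | 1500 | 1200 | 360 | 840 | 41.7 |
| 70 | 1750 | 900 | 420 | 480 | 35.7 |
| 74.9 | 1872.5 | 753 | 449 | 304 | 33.4 |

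A lower baseline raises both prescriptions equally. At 50 kg with m = 1000 mL, P1 = 1.2 × 1500 = 1800 and P2 = 1.2 × 500 = 600; the excess is again 1200 mL/day.

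**The case against.** The strongest reply is that this is an adult formula missing a clause, and that the plan has a check which would catch it. The 24-hour collection is due 2 weeks ± 7 days after randomization, so on days 7 to 21. SPS needs two 14-day periods of missed goals, so about day 28 at the earliest. If the prescription were corrected on the day of collection, the incentive money at risk would be 7 × $1.50 = $10.50 to 21 × $1.50 = $31.50. This timing stands and limits the likely harm. But the adjustment is discretionary, no turnaround is given, and no target is stated for it in the intervention arm. An adolescent who reaches 2.5 L has also met the goal, so nothing requires a reduction.

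Other points:

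- **The goal is a minimum, which 2.5 L satisfies.** True, so the equation overshoots rather than falls short. Section 4.1 nevertheless defines the prescription by what the goal requires, and the equation demands more.
- **The table's 120% rule may already mean 30 mL/kg.** It may, but the cell names no reference goal and the explicit equation says 2.5 L.
- **Most restatements of 30 mL/kg concern the control arm.** Correct for the later part of 4.1, for 6.1.1 and for 7.1.1. Section 3 and the defining sentence in 4.1 apply it to the intervention arm.
- **2.5 L appears alone elsewhere.** It does in section 10.2 and at the start of the control-arm paragraph in 4.1, but neither is a dosing rule.
- **Incentives depend on bottle volume for everyone.** Yes: an adult who reaches the goal with other drinks can also forfeit. Only the size of the gap is particular to this subgroup.
- **The Manual of Procedures may have it right.** It is not among the documents. Whether any adolescent was actually over-prescribed is therefore unknown, but the protocol text needs correcting either way.

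**Conclusion.** The concern holds: section 4.1 is wrong as written for intervention-arm participants under 18 and under 75 kg. Followed literally, it sets an initial prescription above the stated basis by 1.2 × (2500 − 30 × kg) mL/day, more than 300 mL/day in every case. That bound rests only on the protocol's own goal, equation and weight limit; the larger figures depend on the assumed weights. The protocol as a whole favors 30 mL/kg, so the equation is the more likely error.

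The reach is limited. It concerns the initial dose, in a subgroup whose size is not stated; adolescents of 75 kg or more are outside it. The primary analysis and sample size do not change. There is no claim that the volume is unsafe; section 2.3.1 rates the likelihood of hyponatremia as low. It should still be corrected, because it is a dosing instruction for minors that disagrees with its own definition.

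**What to change.** In section 4.1, give two equations:

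- Under 18 and under 75 kg: Initial Fluid Prescription = 1.2 × (30 mL/kg × weight − median urine volume).
- All others, including adolescents of 75 kg or more: 1.2 × (2.5 L − median urine volume), as now.

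In section 6.1.1, state that the baseline deficit is measured against this age- and weight-specific goal, and refer the Week 2 modification to the same goal. Check the Manual of Procedures and the prescription calculator to see how adolescent prescriptions have been set. If the investigators do intend 2.5 L for these participants, leave the equation and correct the stated goal wherever it appears.

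The cost is one line in 4.1, a few words in 6.1.1 and a check of the calculator.
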